Official Title: Movement-Oriented Behavioral Activation (MOBA) to Reduce Stationary Behavior

DUHS IRB Application Version 1.13

Pro00108020

Approval Date: 09/09/2022

NCT04892147

**Aim 1:** Determine feasibility and acceptability of a 10-week group MOBA intervention for individuals with excessive stationary behavior compared to waitlist control.

**Aim 2:** Assess activity and mobility changes following a 10-week group MOBA intervention for individuals with excessive stationary behavior compared to waitlist control.

**Hypothesis:** Individuals completing MOBA will have greater (1) improvement in physical performance, (2) reduction in sedentary time, and (3) increase in daily step count after 12 weeks compared to the control group.

**Aim 3:** Examine changes in activation, avoidance, and perceived barriers to physical activity after a 12-week group MOBA intervention for individuals with excessive stationary behavior compared to waitlist control.

**Hypothesis:** Individuals completing MOBA will have greater (1) increase in activation, (2) decrease in avoidance, and (3) decrease in self-reported barriers to physical activity after 12 weeks compared to the control group.

## Background & Significance

- Should support the scientific aims of the research

Stationary behavior, defined as excessive sitting and/or standing without ambulation, is associated with multiple morbidities acquired by adults through the lifespan that lead to loss of mobility and diminished functional independence in older adulthood. The prolonged lack of movement that characterizes stationary behavior is associated with health risks independent of the health benefits of exercise. The attributes and antecedents of stationary behavior are distinct from exercise as well. This highlights a **critical need** for interventions that are specific to encouraging the regular movement-oriented behaviors needed to reduce the risks of prolonged stationary time, and which account for the key settings where these behaviors occur. Identifying and engaging the behavioral mechanisms that uniquely drive stationary behavior across settings will be essential to achieving lasting behavioral change.

Pervasive approaches to changing stationary activity have two weaknesses: they are overreliant on external motivators to produce behavior change, and they devote insufficient attention to the range of settings in which the behaviors occur. The current study is grounded in reinforcement sensitivity theory (RST), which was developed to explain internal motivational processes in responding to environmental stimuli. RST encompasses two primary motivational systems: the behavioral inhibition system (BIS) and the behavioral activation system (BAS). The BIS guides behavior in response to aversively conditioned stimuli, whereas the BAS guides behavior in response to rewarding stimuli. From the perspective of RST, excessive stationary behavior reflects a learned avoidance of movement resulting from aversive barriers to activity and lack of contact with rewards that activate alternative responses. The rationale of the proposed study is that an intervention based on behavioral activation therapy (BA), which was originally developed to treat depression, can reduce the avoidance that perpetuates stationary behavior by systematically engaging individuals in personally valued and rewarding non-stationary alternatives.

The **significance** of the proposed study, "*Movement-Oriented Behavioral Activation (MOBA) to Reduce Stationary Behavior*," is that it addresses an important public health need for a cross-cutting intervention to reduce stationary behavior. It is significant that the intervention occurs in the setting of an occupational health program, which provides close contact to work-related risk factors like stationary behavior. The significance of the occupational health approach is also related to the pilot cohort, which will be predominantly African American. Unequal access to preventative health services among minorities is a problem in this country, and workplace interventions can be an important strategy in addressing this disparity. Our choice to target stationary behavior rather than the conventional sedentary behavior (excessive sitting) is significant as well. Emerging evidence indicates that prolonged passive standing is as common in workplaces as excessive sitting and has comparable risks to health and mobility; thus, interventions targeting change in the common risk behavior-- lack of ambulatory movement-- will be more potent and translatable than those targeting either behavior alone. The significance of the proposed research is enhanced by **innovative elements:** 1) MOBA is a novel approach to changing stationary behavior, particularly the intrinsic, person-centered principles of behavior change that are underemphasized in existing interventions; and 2) the intervention is innovative in its inclusion of an ecological framework, the Behavior Settings Model, which allows closer contact between personally valued activities and the multiple settings in which stationary behaviors occur.

## Design & Procedures

- Describe the study, providing detail regarding the study intervention (drug, device, physical procedures, manipulation of the subject or the subject's environment, etc.). Discuss justifications for

placebo control, discontinuation or delay of standard therapies, and washout periods if applicable. Identify procedures, tests and interventions performed exclusively for research purposes or more frequently than standard of care. Include alternative therapies, concurrent therapies discontinued per protocol, risk benefit ratio, and use of tissue/specimens. Discuss monitoring during washout periods if applicable. Include brief description of follow-up, if any.

#### Overview.

The study uses randomized waitlist-control design. We propose to randomly assign half of participants to (a) 10 weeks of MOBA intervention, and half of participants to (b) a 10-week waitlist, followed by 10 weeks of MOBA.

**Intervention.** MOBA is adapted from established protocols to integrate traditional behavioral activation (BA) principles with strategies to incorporate values-based, goal-directed movement into daily routines. The BA content of MOBA is adapted from co-investigator [name] intervention Behavioral Activation Therapy for Anhedonia (BATA). MOBA reduces depression-related content relative to BATA and increases focus on values that engage individuals in movement-related activity. MOBA is designed as a group intervention to leverage the reward value of social contact, and the positive influence of group problem-solving and accountability on behavior change. MOBA preserves the principles and general sequence of sessions used in BATA, but incorporates movement-oriented content: (a) provide psychoeducation about risks of physical inactivity, behavioral barriers to activity, and rationale for the treatment approach; (b) explore personal values, non-stationary, movement-oriented activities that support those values, and a hierarchical plan for goal attainment; (c) identify and assign weekly activities related to the valued goals; (d) address common barriers to engagement with valued activities including avoidance, low behavioral initiation, and an overemphasis on felt motivation as a prerequisite for action; and (e) monitor, support, and reward achieving behavioral goals. Content unique to MOBA includes: 1) demonstration and participation in physical activities that provide alternatives to stationary behavior, including select activities used in a previous study with the Dining Services cohort (e.g., stairs, body-weight squats, knee raises), and 2) generation of person-centered strategies for integrating movement-oriented activities into daily routines across the three domains of the Behavior Settings Model: 1) workplace sitting/prolonged standing, 2) screen-focused home activities, 3) time spent sitting in automobiles. Weeks 1-4 address topics a-c; weeks 5-12 address topics d-e. MOBA will be facilitated by a clinician ([name]) and a wellness educator ([name]), who will be trained on the MOBA treatment manual. The facilitators' role is to provide teaching, support, encouragement, and guidance throughout the intervention. Weekly sessions will take place in a dedicated conference room near the workplace, during the last hour of the workday (4-5 pm), and is counted as paid time at work.

#### Assessments.

**Pre-intervention focus group.** Separately, and prior to the enrollment in the intervention, we plan to conduct a small focus group of individuals (N = 8-10) from the Duke Dining Service staff in order to (1) better understand perspectives and experience with physical activity; (2) gauge interest in aspects of the study, and (3) understand format preferences for presenting and collecting information. The goal is to gather information to improve delivery of the intervention to participant stakeholders. Individuals who participate in the focus group are not under any obligation to participate in the intervention.

Feasibility and acceptability. We plan to collect multiple sources of information to provide information about feasibility and acceptability:

(1) We will document our challenges and decisions across all aspects of the study (e.g., recruitment, engagement, obstacles to enrollment) to optimize the translation of our findings; (2) We will collect descriptive data on adherence and participant engagement; (3) We will collect and characterize descriptive information on experience, perceived benefits, and satisfaction; (4) We will conduct focus groups with participants, and those who declined to participate, to better understand "what worked" and "what needs work" with respect to the intervention. We will consult with Duke Roybal Center intervention experts for input on our approach. Fidelity to the treatment will be assessed by [name], who does not lead groups, but will review taped sessions to document adherence (e.g., whether content described in treatment manual is presented during sessions).

Mobility testing. Short Physical Performance Battery (SPPB) will assess lower extremity function and mobility. The 6-Minute Walk Test (6MWT) will assess functional exercise capacity. These measures will occur at Baseline and Week 10.

Mechanisms of change. The Behavioral Activation in Depression Scale (BADS) will assess state characteristics of avoidance and activation. This measure will be administered at baseline and week 5. The Barriers to Being Active Quiz will assess perceived barriers to regular movement-oriented activity. These measures will be administered at baseline and post-intervention.

Stationary behavior. With no validated questionnaire specific to stationary behavior, self-reported sedentary activity will be assessed at baseline/post-assessment, and weekly during the intervention using the Past-Day Adults' Sedentary Time questionnaire (PAST). The PAST assesses multiple domains of sedentary behavior over the past day; it was found to have the highest correlation to device-based activity compared to other questionnaires. The PAST will be administered at baseline, weekly, midpoint, and post

assessment. Device-based tracking. Participants will wear an Actigraph Actilife 6 accelerometer on the right hip for 7 days prior to MOBA participation. This period will represent the pre-intervention control activity condition for each participant. Participants will similarly wear the Actigraph for 1 week post-intervention. The main outcomes of device-based tracking will be percent change in step count per day, with secondary measures including total activity count, and physical activity energy expenditure.

MOBA intervention sessions will occur weekly.

The following questionnaires will also be administered. PHQ-9 will be collected at baseline and week 10, which is post assessment. Physical Activity Readiness will be collected at baseline. The Brief Health Questionnaire will be collected at baseline and week 10. At the final session, a MOBA Class Feedback form will be completed by the participants.

As shown in Table 1, participants will complete a baseline assessment administered by a fitness specialist that includes questionnaires and mobility testing. These assessments will be repeated at end of the intervention. Additionally, the wait-list control group will complete a third assessment at the end of their 02-week participation in MOBA.

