**Table 1. Study assessments**

Aim 1 (pre- and post- intervention)	Acceptability & feasibility: Characterize and document process measures of intervention engagement; descriptive data (e.g., % attendance, % homework completion); participant experience questionnaires, focus groups
Aim 2 (pre- and post- intervention)	Mobility: SPPB, 6MWT, Activity: Actigraph average steps per day, PAST (subjective activity)
Aim 3 (pre- and post- intervention)	Activation/Avoidance: BADS, Barriers: BBAQ
Note: Wait-list control group will be assessed at 3 timepoints: baseline (at waitlist), pre-intervention, post-intervention	

April 6, 2022 An amendment to remove the participant initials from the last page of the consent is incorporated to prevent consent deviations.

May 16, 2022 An amendment to request permission for a magazine article e.g., Work at Duke, to be written about the MOBA project. This article will include pictures of participants and interviews, if they agreed. These pictures would require a release to other purposes, such as presentations or an eventual website. It is hoped that the article could be written with the next set of assessments, which is scheduled near the end of June. By participating in the article, participant's involvement would no longer be confidential.

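### The device paragraph gives the waitlist arm two Actigraph wears where Table 1 implies three; read literally, its change in steps over the waitlist cannot be computed.

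*Combined protocol and SAP*

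**What the plan says.** The Overview under Design & Procedures randomises half of participants to 10 weeks of MOBA and half to a 10-week waitlist followed by 10 weeks of MOBA.

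The device-based tracking text under Assessments is the only operational instruction on wearing the accelerometer. It says "Participants will wear an Actigraph Actilife 6 accelerometer on the right hip for 7 days prior to MOBA participation", and adds "This period will represent the pre-intervention control activity condition for each participant". The second wear is given as "Participants will similarly wear the Actigraph for 1 week post-intervention". On the endpoint it says "The main outcomes of device-based tracking will be percent change in step count per day". No separate schedule is given for the waitlist arm.

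Table 1 lists Actigraph steps among the Aim 2 measures, and its note reads "Wait-list control group will be assessed at 3 timepoints: baseline (at waitlist), pre-intervention, post-intervention". The closing paragraph of Assessments agrees with three assessments: "the wait-list control group will complete a third assessment at the end of their 02-week participation in MOBA". (The week count printed there is evidently a slip and does not matter here.) That paragraph describes the baseline assessment in terms of questionnaires and mobility testing and does not name the accelerometer.

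The Aim 2 hypothesis on the opening page expects a larger rise in daily steps with MOBA than with control. The analysis plan for Aim 2 examines Actigraph change from baseline to post-intervention without defining either term for the waitlist arm.

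**The concern.** Two wears cannot supply three timepoints. If staff follow the device text as written, a waitlist participant first wears the device in the week before their own MOBA course, about 10 weeks after randomisation. There is then no step count at the start of the waitlist, and a missed baseline week cannot be recovered later. What would be lost is the waitlist arm's percent change in steps over the untreated period. That is the control counterpart of the main device outcome, and it is what the Aim 2 step hypothesis needs.

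The undefined baseline in the analysis plan adds to the risk. If baseline means the pre-MOBA week in both arms, both arms' changes span MOBA, and a difference between them would not estimate the effect of MOBA.

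**Working it through.** The plan states no figure on this point to reproduce. The first check is which wears each reading supplies, in approximate weeks from randomisation, using the 10-week waitlist and 10-week course from the Overview.

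| Reading | MOBA arm | Waitlist arm | Waitlist change, weeks 0 to 10 |
|---|---|---|---|
| Device text, literal | 0, 10 | 10, 20 | not computable (no week 0) |
| Device text, single pre-MOBA wear placed at randomisation | 0, 10 | 0, 20 | not computable (no week 10) |
| Shared clock: both arms at baseline and week 10 | 0, 10 | 0, 10 | computable, but no post-MOBA wear in the waitlist arm |
| Table 1 with its note | 0, 10 | 0, 10, 20 | computable |

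Only the Table 1 reading gives both the control change and the waitlist arm's change across MOBA.

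**Wear-weeks**, with 16 per arm (Selection of Subjects, sample size):
- Device text, literal: 2 × 32 = 64.
- Table 1: 2 × 16 + 3 × 16 = 80.
- Difference: 16.

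**Precision at week 10.** Let r be the correlation between baseline and week-10 steps. The documents do not give it, so r = 0.5, 0.7 and 0.8 are assumed. Standard errors (SE) of the between-arm difference are in units of the SD of steps (of log steps if percent change is analysed), with equal SDs at both times, 16 per arm and no attrition.
- Week-10 values only: SE = √(2/16) = 0.354, whatever r is.
- Change scores: SE = √(2(1 − r)) × 0.354.
- Week-10 values adjusted for baseline (a method the plan does not specify): SE = √(1 − r²) × 0.354.

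| Assumed r | Week 10 only | Change score | Baseline-adjusted |
|---|---|---|---|
| 0.5 | 0.354 | 0.354 | 0.306 |
| 0.7 | 0.354 | 0.274 | 0.252 |
| 0.8 | 0.354 | 0.224 | 0.212 |

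Below r = 0.5, unadjusted change scores are less precise than week-10 values alone; at r = 0.3 the SE is √1.4 × 0.354 = 0.418. The baseline wear therefore always makes the control change available, but how much precision it adds depends on r and on the analysis.

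**The case against.** The strongest reply is that the plan already covers this. The Assessments text refers to Table 1, whose note names a baseline at the start of the waitlist. The mobility tests and the PHQ-9 are also described in two-point shorthand, so the device text may be no more than that. It omits a randomisation wear; it does not forbid one. This stands, and is why Table 1 is taken as the probable intent.

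A second reply is the shared-clock reading. The PHQ-9 text equates week 10 with the post assessment, and the waitlist arm's assessment after MOBA is called its third, so its first two fall at about weeks 0 and 10. Wears at those two points would keep the control change. This too is possible. But it sits badly with wording that ties the first wear to MOBA for each participant, and it leaves the waitlist arm without the post-MOBA wear that Table 1 implies. That the text allows such different schedules is the reason to reconcile it.

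A reader might infer more than the documents support:
- **That the plan as a whole has no control change in steps.** Table 1 points the other way.
- **That the plan subtracts one arm's MOBA change from the other's.** The Aim 2 analysis plan specifies no such subtraction.
- **That stated pilot objectives fail.** Data Analysis & Statistical Considerations promises group changes against an MCID such as 500 steps per day, and SDs of activity outcomes. It does not promise an MCID summary or an SD for untreated change specifically. Single-timepoint SDs survive every reading.

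**Conclusion.** The concern holds as a conflict between the device text and Table 1. Under the literal reading, none of the 16 planned waitlist participants would have a computable change in steps over the waitlist; under Table 1 all 16 could, before attrition. The literal reading still leaves a valid randomised comparison of step counts at about week 10 and each arm's change across MOBA.

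Severity is modest. The plan says its sample is too small for formal testing of group differences and calls those comparisons preliminary, and the intended schedule can probably be read from Table 1. It is still worth fixing, because a missed baseline wear cannot be recovered and the repair is small. The schedule finding rests only on the documents' own timings. The precision figures rest on an assumed correlation and equal SDs, so they illustrate the possible gain and do not determine the severity.

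**What to change.** - **Device-based tracking text:** state wear weeks by arm to match Table 1. Both arms wear the device for 7 days at randomisation baseline. The MOBA arm wears it again after MOBA. The waitlist arm wears it again just before MOBA and again after it.
- **Analysis plan for Aim 2:** define the control change as waitlist baseline to pre-MOBA, and compare it, as preliminary, with the MOBA arm's change from baseline to post-intervention.
- **Data already collected:** first record which wears exist. A May 2022 entry below Table 1 refers to "the next set of assessments, which is scheduled near the end of June", and this version was approved on 09/09/2022, so some wears may already be complete. If the waitlist baseline wears were not collected, report the week-10 comparison and do not present the waitlist arm's change across MOBA as a control change.

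The cost is wording in two places, plus at most 16 wear-weeks beyond the literal device text, which Table 1 already implies. There is some added participant burden and demand for devices in the baseline week; the documents do not say how many devices are available.

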### Data Analysis & Statistical Considerations

- Describe endpoints and power calculations. Provide a detailed description of how study data will be analyzed, including statistical methods used, and how ineligible subjects will be handled and which subjects will be included for analysis. Include planned sample size justification. Provide estimated time to target accrual and accrual rate. Describe interim analysis including plans to stop accrual during monitoring. Phase I studies, include dose escalation schema and criteria for dose escalation with definition of MTD and DLT.

Sample size was based on previous recommendations from Lancaster et al. that targeting approximately 30 participants is a pragmatic standard for feasibility trials. While we recognize this sample size will not allow us to derive meaningful effect size estimates for between-group comparisons in this pilot study, it will be useful in determining the acceptability of the proposed intervention and deriving variance metrics (e.g., standard deviation of physical activity outcomes) for the purposes of future effect size estimation. We acknowledge that the proposed sample size is not adequate for formally testing group differences or effect size metrics. We will therefore (a) interpret these comparisons as preliminary, (b) characterize effect sizes for pre-to-post changes within each group separately, and (c) characterize group changes in actigraphy using contemporary minimum clinically important difference (MCID) metrics (e.g., 500 steps / day).

**Analysis plan for Aim 1.** We plan to collect multiple sources of information to provide information about feasibility and acceptability: (1) We will document our challenges and decisions across all aspects of the study (e.g., recruitment, engagement, obstacles to enrollment) to optimize the translation of our findings; (2) We will collect descriptive data on adherence and participant engagement; (3) We will collect and characterize descriptive information on experience, perceived benefits, and satisfaction; (4) We will conduct focus groups with participants, and those who declined to participate, to better understand "what worked" and "what needs work" with respect to the intervention. We will consult with Duke Roybal Center intervention experts for input on our approach. Areas of efficacy: We will use data from the PAST questionnaire to identify which domains of activity are most and least responsive to MOBA. Fidelity to the

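### Step-count change is measured against each participant's own pre-MOBA week, which cannot separate MOBA from time, and the randomised contrast is not spelled out

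*Combined protocol and SAP*

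**What the plan says.** The Overview states: "The study uses randomized waitlist-control design". Half of the participants start MOBA at once. The other half are assigned to "b) a 10-week waitlist, followed by 10 weeks of MOBA". The hypotheses under the aims are worded against the control group.

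The device paragraph in Assessments is organised differently. It says: "Participants will wear an Actigraph Actilife 6 accelerometer on the right hip for 7 days prior to MOBA participation", and then of that week: "This period will represent the pre-intervention control activity condition for each participant". The second wear is tied to the end of treatment: "Participants will similarly wear the Actigraph for 1 week post-intervention". On the outcome it says: "The main outcomes of device-based tracking will be percent change in step count per day".

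Table 1 lists Actigraph steps under Aim 2 as a pre- and post-intervention measure. Its note gives the waitlist arm three assessments: at waitlist entry, before MOBA and after MOBA.

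Data Analysis & Statistical Considerations accepts that the sample is too small for formal testing of group differences. It will treat those comparisons as preliminary, "characterize effect sizes for pre-to-post changes within each group separately", and describe group actigraphy change against a minimum clinically important difference, with 500 steps/day as the example. The Aim 2 analysis plan describes Actigraph results only as change from baseline to post-intervention. No between-arm model or period term is named.

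**The concern.** A person's own earlier week is a baseline. As a control condition it works only if steps would have stayed level for 10 weeks without MOBA, and the plan gives no reason to expect that. Participants are campus dining staff, chosen for their work demands, so a change in work content or in off-work activity would act directly on the outcome. One dated entry, below Table 1, places a round of measurements "with the next set of assessments, which is scheduled near the end of June". A phase that begins or ends then could straddle a change in campus activity.

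What is at stake is the interpretation of the step result. Because the plan plays down between-group comparisons and turns to within-group change, the figures most likely to be carried into a later trial are the ones that a time trend biases, upward or downward. The randomised waitlist, which could remove a common trend, is not tied to the step outcome in the analysis text.

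**Working it through.** **The plan's own figures.** 2 x 16 = 32 recruited. With 23% attrition, 32 x 0.77 = 24.6 completers, or 16 x 0.77 = 12.3 per arm; I use 12. The sample size rests on a rule of thumb, with no SD, effect size or power, so there is no precision figure to reproduce.

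**What each change estimates.** Let T be the MOBA effect, S1 the mean change without MOBA over weeks 0-10, and S2 the same over weeks 10-20.

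| Change | Estimates |
|---|---|
| MOBA arm, baseline to post | T + S1 |
| Waitlist arm, waitlist baseline to pre-intervention | S1 |
| Waitlist arm, pre- to post-intervention | T + S2 |
| First row minus second | T, if S1 is common to both arms |

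Nothing in the design estimates S2. The MOBA arm is assessed at baseline and at the end of treatment, and Participant Remuneration lists only a 2-month interview after that.

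**Is the second row available for steps?** Read literally, the device paragraph times the first wear week to the start of MOBA. For the waitlist arm that is the end of the wait, which leaves no step count at randomisation. The Table 1 note gives that arm a waitlist baseline, but does not say that the device is worn then. The difference in step change exists only on the second reading.

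**Size.** Assumptions not in the documents: SD of change 1,500, 2,000 or 3,000 steps/day, and a shift S of 0 to 1,000 in either direction.

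SE of one arm's mean change = SD/sqrt(12) = 433, 577, 866.

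SE of the between-arm difference = SD x sqrt(2/12) = 612, 816, 1,225, which is sqrt(2) = 1.41 times larger.

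P(mean change >= 500) = 1 - Phi((500 - T - S)/SE). With T = 0:

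| S | SD 1,500 | SD 2,000 | SD 3,000 |
|---|---|---|---|
| 0 | 12% | 19% | 28% |
| +250 | 28% | 33% | 39% |
| +500 | 50% | 50% | 50% |
| +1,000 | 88% | 81% | 72% |
| Between-arm difference, any common S | 21% | 27% | 34% |

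A shift can also hide an effect. With T = 500, the chance is 50% at S = 0. At S = -1,000 it is 1 - Phi(1,000/SE) = 1%, 4% and 12% for the three SDs.

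**Precision of the between-arm difference.** The 95% half-width is 1.96 x SE = 1,200, 1,600 and 2,400 steps/day. Power for a true 500 is about 13%, 9% and 6%. The contrast removes a common shift but remains preliminary.

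**Calendar.** The amendment entry is dated May 2022, so take 20-30 June 2022. A 10-week phase ending then began on 11-21 April; one starting then ends between 29 August and 8 September. If the June round is a week-5 midpoint, the phase runs from 16-26 May to 25 July-4 August and does not begin or end in June. The hypotheses and the session content also refer to 12 weeks, which moves the far end by two weeks.

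**The case against.** The strongest reply is that the trial already has a control. It randomises to a concurrent waitlist, words its hypotheses against that group, assesses the waitlist arm before and after the wait, and disclaims effect inference. That stands, and it answers several stronger readings that a reader might draw:

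- **That a campus-calendar shift will be read as a MOBA effect.** The documents mention no term dates, season or workload change. The size and sign of any shift are unknown, and it could mask an effect as easily as mimic one.
- **That late June must begin or end a MOBA phase.** The entry concerns a magazine article and does not name the round. A full set of assessments fits a boundary visit better, but BADS at week 5 and PAST at the midpoint are also planned.
- **That the two arms carry biases of opposite sign.** This needs a reversible shift and a known June visit. Neither is documented.
- **That the waitlist arm's MOBA phase is offered as a second estimate of the effect.** No section says so. Within-group change for that arm could equally mean change over the wait, which would display a time trend.

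An uncontrolled second phase is also normal in a waitlist design. What the reply does not answer is that the analysis text never states the between-arm contrast for steps, that the device paragraph names a different control, and that the wear schedule may not supply the data the contrast needs.

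**Conclusion.** The point holds in a limited form. As written, the step result is a within-group change from a week labelled as the control condition, and it cannot be separated from anything else that changes over the same 10 weeks. For the first phase this can be repaired with the randomised waitlist, provided that arm has wear weeks at both ends of the wait and any shift is common to both arms. For the waitlist arm's MOBA phase it cannot be repaired, because nothing runs alongside it.

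Under the assumed SDs and 12 completers per arm, a shift equal to the 500-step threshold raises the chance that an inert intervention reaches it from 12-28% to 50%; the between-arm difference stays at 21-34% whatever the common shift. These figures show sensitivity and do not estimate an actual campus effect. Severity is low: this is a feasibility pilot, and it already calls its comparisons preliminary.

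**What to change.** 1. In the data analysis section and the Aim 2 plan, state that the MOBA contrast is the between-arm difference in change over the first phase: MOBA arm baseline to post, against waitlist arm waitlist-baseline to pre-intervention. Report it with a confidence interval and as preliminary.
2. Reconcile the device paragraph with Table 1 so that the waitlist arm's Actigraph week at waitlist baseline is explicit, and call the pre-MOBA week a baseline rather than a control condition. The 10-week and 12-week statements need reconciling too, since they fix the post-assessment date.
3. Label the waitlist arm's MOBA-phase change as uncontrolled and report it descriptively with its calendar dates. Do not interpret either arm's within-group change against 500 steps/day as a MOBA effect.

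Splitting results by term, break or summer would add little. Each arm appears to be one group of 16 with shared weekly sessions, so calendar is tied to arm and phase.

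The cost is wording, recorded wear dates and, if it is not already intended, one more wear week for up to 16 people. The between-arm difference has a standard error about 1.4 times that of a single-arm change, and the waitlist arm's MOBA phase no longer supports an effect reading.
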